## Blood Pressure Safety Protocol

[figure not shown]
\*Symptoms include chest pain or discomfort, shortness of breath, back pain or discomfort, numbness/weakness, change in vision and/or difficulty speaking.

## WatchBP Office AFIB Initializing Procedures

1. Plug the adapter in the wall and plug into the back of the device.
2. On the top of the clinic device is the **on/off** switch. Turn the clinic device on by switching the **on/off** button.

[figure not shown]
3. Press the circular **on/off** button on the lower right of the device to power up the device.
4. Make sure the slider on the front of the device between the 'M' and on/off button is all the way to the left on 'Routine'.
5. Press and hold the **on/off** button for 3 seconds until the device lights up blue, 'Sec' appears, and a flashing number appears. This will allow you to set the interval between readings and the rest period.
6. Next, the resting period time will begin to flash. Press the 'M' button until the '300' appears on the device. This will set the resting period to 5-minutes. Press the **on/off** button to confirm the resting period.

7. Press the 'M' button until the '60' appears on the device. This will set the interval between measurements to 1-minute. Press the **on/off** button to confirm this interval (see 3 in the Figure below).

8. To switch the arm that is being measured (Left or Right; whichever is the participant's non-dominant arm), press and hold the **M** button for 3 seconds.
9. To hide the blood pressure readings, press and hold the **M** button for 7 seconds.
10. Connect the clinic device to the computer using the USB to micro-USB computer cable.
11. Launch WatchBP Analyzer Office software.

[figure not shown]

12. Select 'WatchBP Office AFIB' (see below).

## Better BP Study: Manual of Operations

[figure not shown]
### 13. Create a new patient entry by selecting 'New'.

[figure not shown]
14. Enter the participant's information in window. The Participant ID number will be entered three times in the following text fields: ID number, Last Name and First Name. **Do not enter participant name and Date of Birth and Gender.**

Enter 'NA' for Physician ID, Name, and Surname.

- a. *Participant ID number (required – enter participant ID)*
- b. *Last name (required – enter participant ID)*
- c. *First name (required – enter participant ID)*
- d. *Date of Birth (Leave as pre-filled value 1/1/1900)*
- e. *Gender (Leave as 'Male')*

15. Select 'Save' once you enter their information.
16. Select the participant id number you created (**see screen grab below**).
17. Select 'Routine' measurements.
18. Select the arm (**Left/Right**) the participant will have their clinic blood pressure measured.  
This should be their **non-dominant arm** unless there is some reason it is not possible to use their non-dominant arm. **This should be notated on the Study Visit 1 Form.**
19. Under 'Select the number of measurement(s):' select '3 measurements: take 3 consecutive measurements'.
20. Select 'Hide Record (Device display in both Screen and Routine mode)'. This ensures that participant will not be able to see their blood pressure readings.

21. If taking attended clinic blood pressure, press 'Measure' and remain in the room, but do not talk or interact with the participant. Make sure the 5-minute rest period has begun by looking at the countdown on the device.
22. If taking unattended clinic blood pressure, press 'Measure' and look at the device to make sure the 5-minute has begun by looking at the countdown on the device. Once countdown has started, remind the participant to rest, not talk or move until three blood pressure measurements are taken, then exit the room and return in 10-minutes.

## ABPM Procedures

Use the Better BP Study Visit 2 and Study Visit 3 Data Collection Forms to record information from the second and third study visit.

### Testing the ABPM Device and Fitting Participant with Equipment

1. The appropriate cuff size should be ready (see arm circumference measurement on Study Visit Form 1 to verify correct size). Place the cuff on the participant's non-dominant arm. **If the non-dominant arm cannot be used, use the participant's dominant arm** (this will require using a bladder positioned for the other arm). The cuff must be placed against the skin (not over any clothing). Locate the brachial artery by palpation and mark the skin with a small dot, using a black pen. (The brachial artery is usually found just medial and superior to the cubital fossa, posterior to the biceps muscle and slightly toward the body.) For brachial artery palpation, fingertips or thumb may be used. Refer to the **Participant Instructions**.
2. The research coordinator will explain to the participant that the cuff will feel tight during the first measurement. The participant will be instructed that the ABPM will inflate the cuff to a pressure between 170 and 180 mmHg, but this will only occur on the first reading. Each subsequent reading will go only 20 mmHg higher than the previous systolic reading. The research coordinator will instruct the participant that a tone will go off during the daytime to alert them that a reading is about to occur.
3. During recordings, the participant is instructed to: (1) remain as still as possible, (2) keep his/her arm relaxed at his/her side or at heart level as if in a sling or resting on a table or armrest, and (3) refrain from talking. The research coordinator should demonstrate the appropriate arm positioning to the study participant.
4. Next, a blood pressure reading should be taken using the ABPM device to confirm it is working properly. The research coordinator will press the **On/Off** button and place the device in

'Ambulatory' mode. The purpose of taking an initial reading is to make sure the cuff inflates and deflates as expected. Once one successful reading is acquired, proceed to the next step. If the cuff does not inflate and then deflate, then check that batteries are properly inserted and if so, initialize a new ABPM device for use. Also, if three readings are attempted and all result in errors, then a new ABPM device will be initialized for use. If either of the above occurs, the research coordinator will email [name] ([contact]) to inform them of a non-functioning device.

5. Final fitting of the ABPM device: the non-latex red tubing should go around the back of the participant's neck and come down the dominant side of his/her body. Usually, it is placed underneath the participant's clothing, coming out at the waist or between two button holes of the shirt. The pouch with the ABPM device can be 1) placed in a jacket pocket, 2) hooked onto a belt (using the loop on the back of the pouch), or 3) worn with a shoulder strap connected by 2 black plastic tabs to the inside edges of the pouch.

6. The research coordinator will explain how the ABPM device works to the participant, noting that every 30 minutes the ABPM device will automatically make a BP measurement.

7. The research coordinator will show the participant the phone number for the research team. This is located inside the **Participant Instructions** that will be provided to them. Therefore, the participant can call with any questions or concerns about any of the equipment. Also, the research coordinator will show the participant the number to call for the research coordinator during regular business hours. For after hours' calls, participants will be provided with a cell phone number for one of the study staff members familiar with the study.

8. The participant will be informed that if an ABPM measurement fails, usually because of motion (including driving), talking, or because the arm is not relaxed, the device will attempt another measurement 2 minutes later. If this repeat attempt fails, no further attempts will be made until the next scheduled reading 30 minutes later.

9. The participant will then be told that in the very unlikely event the cuff does not deflate after a reading, the **On/Off** circular button on the ABPM device should be pressed (shown in picture above). The cuff should automatically deflate. If the cuff still does not deflate, the participant should turn off the device. To do so, they will hold the **On/Off** circular button for three seconds. Once the cuff has deflated, the participant can push the **On/Off** circular button to turn the device back on. Then, they can resume wearing the device as before (i.e., they can place the device back in the pouch) and their blood pressure should be measured every 30 minutes.
10. At this time, the research coordinator should tell the participant that the ABPM device will continue to obtain recordings during sleep. The participant is told that the device is programmed so that during the daytime, the ABPM device will emit a tone immediately before each BP measurement to signal that the cuff is about to be inflated; however, during the participant's usual sleep hours, this tone is turned off.
11. The research coordinator will then ask the participant to avoid getting the ABPM device wet, but mention that there is no personal danger to the participant if the ABPM device does get wet. The research coordinator will ask the participant to keep the equipment dry at all times. We prefer that participants not shower, swim, or go to the gym during the 24 hours they are wearing the ABPM device. However, if this is absolutely not possible, then the equipment should be removed before showering, swimming or engaging in vigorous activity. Each time the participant removes equipment he/she should log the time the equipment was removed as well as the time it was put back on (**see ABPM Device Log; Appendix 2**).
12. The research coordinator will show the participant how to remove and put back on the ABPM device.
13. To remove ABPM device, the research coordinator instructs the participant to pull the

Velcro flap away from his/her body and slide the cuff down off his/her arm.

14. The participant is told to gently pull the white tubing over his/her head and away from his/her body.

[figure not shown]
15. To put the ABPM device back on, the participant is instructed to place the cuff on his/her non-dominant arm, lead the white tubing behind his/her neck and let it rest by his/her opposite side. The arrow on the bottom of the cuff should be pointing down and situated over the brachial artery, about 1 inch above the bend in the elbow. If the participant does not know where the brachial artery is located, the research coordinator will offer to mark it with a pen (if this has not already been done) so that the participant can be assured the cuff is situated properly.

16. The researcher will ask the participant to demonstrate to them how to properly remove and replace the device before moving forward.

[figure not shown]
17. Next, the research coordinator will show the participant how to remove and replace the Actiwatch device (see **Participant Instructions**).

### O3 Ambulatory Device Initializing Procedures

[figure not shown]
1. On the front of the ABPM device (**lower right**) is the **on/off** (circular) button. Turn the ABPM device on by pressing the **on/off** button.

2. Connect the ABPM device to the computer using the USB to micro-USB computer cable.
3. Launch WatchBP Analyzer O3 software.
4. To ensure that the data from a previous participant has been cleared, select 'Clear Memory'.

5. Select 'Ambulatory settings' to set the participant id number, day period, night period, intervals between readings, highest inflation pressure, alert noise, and hiding BP data.
  - a. *Participant id number – corresponds to record id number in REDCap*
  - b. *Day period – participant reported awake time to sleep time*
  - c. *Night period – participant reported sleep time to awake time*
  - d. *Intervals – 30 minutes during day period and night period*
  - e. *Highest inflation pressure – enabled at 180 mmHg*
  - f. *Select 'Hide BP data'*
  - g. *Silent Mode – Make sure that this is checked for each participant*
6. Once everything is entered, select 'Program'.

[figure not shown]

**Buffer:**

We will buffer both the sleep and awakening times by at least 30 minutes so that the tone will not awaken participants. Remember the sleep/awake time settings on the O3 ABPM device can only be set to the hour. Take the participant's anticipated wake-up time, add 30 minutes, and round up to the next hour; take the participant's anticipated sleep time, subtract 30 minutes, and round down to the next hour. Here are three examples of how sleep and awake times will be set during the initialization process:

[figure not shown]
- A participant who reports going to bed at 11pm and waking up at 6am will have their sleep time set to 10pm to 7am.
- A participant who reports going to bed at 11:30pm and waking up at 6:30am will have their sleep time set to 11pm to 7am.
- A participant who reports going to bed at 11:15pm and waking up at 6:15am will have their sleep time set to 10pm to 7am.

[figure not shown]
7. A program warning will pop-up (**screen grab below**), select 'Yes'.

8. A message will appear that programming was successful, press 'Okay'.

9. Disconnect the device from the computer and make sure the slider on the right side of the device is on 'Ambulatory' mode.
10. Once you see 'Ambulatory' appear on the screen and a countdown at the bottom right of the device appears, the ABPM device is ready to be used by the participant.

## HBPM Procedures

Use the Better BP Study Visit 2 and Study Visit 3 Data Collection Forms to record information from the second and third study visit.

### Testing the HBPM Device and Fitting Participant with Equipment

1. The appropriate cuff size should be ready (see arm circumference measurement on Study Visit Form 1 to verify correct size).
2. Demonstrate to the participant how to place the cuff on their non-dominant arm. **If the non-dominant arm cannot be used, use the participant's dominant arm** (this will require using a bladder positioned for the other arm). The cuff must be placed against the skin (not over any clothing). Locate the brachial artery by palpation and mark the skin with a small dot, using a black pen. (The brachial artery is usually found just medial and superior to the cubital fossa, posterior to the biceps muscle and slightly toward the body.) For brachial artery palpation, fingertips or thumb may be used.
3. The research coordinator will explain to the participant that the cuff will feel tight during the first measurement. The participant will be instructed that the HBPM will inflate the cuff to a pressure between 170 and 180 mmHg, but this will only occur on the first reading. Each subsequent reading will go only 20 mmHg higher than the previous systolic reading.
4. The research coordinator will inform the participant that to begin their recordings they should press and hold the **On/Off** button for 3 seconds to begin the initial reading.
5. Next, a reading should be taken to confirm the device is working properly. The research coordinator will press the **On/Off** button and place the device in 'Casual' mode. The first reading will be based on the device's internal algorithm. The purpose is to make sure the cuff inflates and deflates as expected. Once one successful reading is acquired, proceed to the next step. If the cuff does not inflate and then deflate, then check that batteries are properly inserted and if

so, initialize a new HBPM device for use. Also, if three readings are attempted and all result in errors, then a new HBPM device will be initialized for use. If either of the above occurs, the research coordinator will email [name] ([contact]) to inform him of a non-functional device.

6. The research coordinator will explain how the HBPM device works to the participant. Note that the HBPM device will automatically take a blood pressure reading at 2, 3, and 4 hours after the initial reading.

7. At this time, the research coordinator tells the participant that the HBPM device will continue to obtain recordings during sleep.

8. The research coordinator will show the participant the phone number for the research team is located inside the **Participant Instructions** that will be provided to them. Therefore, the participant can call with any questions or concerns about any of the equipment. Also, the research coordinator will show the participant the number to call for the research coordinator during regular business hours. For after hours' calls, participants will be provided with a cell phone number for one of the study staff members familiar with the study.

9. The research coordinator will ask the participant to keep the equipment dry at all times. The participant should log the time they went to bed and the time they wake up in the morning. If the participant removes equipment during the night, he/she should log the time the equipment was removed as well as the time it was put back on (**see HBPM Device Log; Appendix 2**).

10. The research coordinator will show the participant how to put the HBPM device on, the participant is instructed to place the cuff on his/her non-dominant arm, lead the white tubing behind his/her neck and let it rest by his/her opposite side. The arrow on the bottom of the cuff should be pointing down and situated over the brachial artery, about 1 inch above the bend in the elbow. If the participant does not know where the brachial artery is located, the research coordinator will offer to mark it with a pen (if this has not already been done) so that the

[figure not shown]
participant can be assured the cuff is situated properly. The research coordinator will inform the participant that they should place the device on their nightstand by the bed or under their pillow.

11. The researcher will ask the participant to demonstrate to them how to properly place the device before moving forward.

[figure not shown]
12. Next, the research coordinator will show the participant how to remove and replace the Actiwatch device.

## WatchBP Home N Initializing Procedures

[figure not shown]
1. Connect the clinic device to the computer using the USB to micro-USB computer cable.

2. Launch WatchBP Analyzer Home N software.

[figure not shown]

3. Select the “Set Patient ID” button on the main screen.

4. Enter the participant record id number.

5. Select 'Program'.

[figure not shown]
[figure not shown]

6. A message will appear that says 'Send ID successful', press 'Okay'.

7. Disconnect the device from the computer.

8. Make sure the device is in 'Nocturnal' mode by sliding the slider on the right side of the device to 'Nocturnal'.

## Better BP Study: Manual of Operations

[figure not shown]

## Fitting the Actiwatch

1. Next, the research coordinator will explain to the participant how the Actiwatch works. The participant will be told the Actiwatch should be worn on the wrist of the non-dominant arm, the same arm as the BP cuff, and that it will provide a measure of his/her overall sleep.
2. The research coordinator will place the Actiwatch on the wrist of the participant's non-dominant arm, and then ask the participant to avoid getting the Actiwatch wet. We would prefer that the light sensor on the device be on the outside of the wrist.
3. After reviewing this information, the research coordinator will ask the participant if they have any questions regarding the Actiwatch.
4. Next, the research coordinator will review the **Participant Instructions (see Appendix 3)** with the participant and remind him/her that if anything should happen with the equipment in the next 24 hours, he/she should contact the research team immediately using one of the phone numbers provided.
5. The research coordinator will thank the participant and confirm how the participant will bring back the ABPM/HBPM and Actiwatch devices along with the Device Log (**Appendix 2**) (see procedures for returning the equipment and Device Log below). **Be sure to instruct the participant where he/she should record their sleep and wake times on the Device Log (Appendix 1), and any times the equipment was removed.**
6. Finally, the participant should be given the **Participant Instructions (see Appendix 3)**. The participant should be informed of how to contact the research coordinators if he/she has a question/concern. The location of this information in the Participant Instructions should be shown to the participants.

[figure not shown]
## Configure/Initialize the Actiwatch

1. Make sure before using an Actiwatch device that it is fully charged. When the watch is on the charger, a solid green light indicates the watch is fully charged. A blinking light indicates that the watch is not fully charged. Before starting the process below, place the Actiwatch to be used in the charging station. Open the Philips Actiware 6.02 software (NOTE: the same computer must be used to initialize the ABPM and Actiwatch; ideally the data would also be downloaded to the same computer). Then select “Communications” on the menu bar at the top of the window, and select “Actiwatch Console”, which will bring up the “Actiwatch Communications Console”.

[figure not shown]

[figure not shown]
2. Select the “Actiwatch 2 device” and then select the “Configure” button at the bottom of

the screen.

[figure not shown]

3. Select “New Subject” button (see screen grab 3A below). Under the “Identity” field, type the participant ID (see screen grab 3B below). Do not enter the date of birth or gender. Leave as the default settings. Then under the “Last Name” field, enter the participant ID again (see screen grab 3B below). Then select the “OK” button.

[figure not shown]

[figure not shown]
4. Then the “Configure Actiwatch” window will be shown on the screen. Select the “Next” button.

5. Make sure that the “Epoch Length” is 15 seconds and the “Logging Mode” is “Activity and Photopic Light”. Make sure that the “Maximum Recording Time” is at least 3 days. Select the “Next” button.

6. Select the check box for “Start collecting data as soon as possible”. The “Data Collection Duration” should be set at 7 days. Select “Configure” button. Then select “Continue” button. When done, hit “OK”.

[figure not shown]
### **Instruction for Returning the ABPM/HBPM Device and Actiwatch**

To return the ABPM/HBPM and actigraphy (Actiwatch) devices and the participant device log, participants must return to the clinic the day after performing the ABPM or HBPM (**REQUIRED**).

18. Once finished, remove the ABPM device from the computer by disconnecting it from the USB to micro-USB computer cable connector. **Turn off** the ABPM device and remove the batteries.

**If at least 35 readings are obtained, ask the participant to complete the “POST ABPM QUESTIONNAIRE”.**

Ask the participant to complete questions regarding the quality of sleep over the 24-hour monitoring period and the comfort of the ABPM device.

[figure not shown]
**If at least 35 readings are NOT obtained, ask the participant to repeat the ABPM monitoring period for one night.**

**If they say yes**, clear the memory and re-initialize the device with the participant's id number and adding the text ('-2') at the end (i.e. - 1101-2). Replace the device on the participant and review the instructions again. Give the participant a new ABPM device log to complete.

**If they say no**, ask the participant to complete questions regarding the quality of sleep over the 24-hour monitoring period and the comfort of the ABPM device using the “POST ABPM QUESTIONNAIRE”.

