9. Participants will be given instructions for placing (Home N) or replacing (O3 ABPM) the device if it has to be removed.
10. Participants will be given a phone number to call if they have any questions during the monitoring period.
11. Participants will be given the appropriate (ABPM or HBPM) device log to fill out. This form captures the time a participant goes to sleep and awakens. Additionally, this form can be used to document any time when a participant removes the device and puts it back on.

12. The Actiwatch device will be fitted.
13. The next day, participants will return the device and device log, complete either the post-ABPM or post-HBPM questionnaire based on what device was worn, and be fitted for the opposite device (either O3 ABPM or Home N).
14. At the last visit, participants will return the device and device log and complete either the post-ABPM or post-HBPM questionnaire based on what device was worn.
15. Participant will complete the comparability questionnaire.
16. Participants will complete a non-fasting blood draw and spot urine.
17. Participants will complete an echocardiogram. If the echo lab does not have availability for that day, schedule their echocardiogram within the next two weeks.

Participants will return to the clinic the next day to return their ABPM/HBPM devices and actigraphy (Actiwatch) devices and the participant device log.

Upon returning the devices, the technician will:

1. Review the device log with the participant, verifying times the participant went to sleep, woke up, and took device(s) off. If the participant does not return the device log (or it is blank), be sure to fill it out at the return visit.
2. Download the data from the ABPM, HBPM, and actigraphy devices.
3. Confirm that at least 35 of planned ABPM readings are valid or all three HBPM readings are valid. If this is not the case, the participant will be offered the opportunity to complete a second ABPM or HBPM (along with actigraphy and filling out the participant device log).

For participants who have a complete ABPM (or for those who have the device picked up at their house), the participant device log will be checked for completeness, scanned and saved electronically. Next, we will administer the post-ABPM study visit form.

Upon completion of the physical exam and echocardiogram, we will then process their reimbursement. The participants will receive reimbursement through the mail.

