**When clinic staff will handle the return of the ABPM/HBPM:**

For participants for whom the device is picked up at their house or who mail in the device, the forms/device will be delivered to the clinic staff. The staff member will check to confirm that at least 35 valid ABPM readings or 3 valid HBPM readings were obtained and that the post-ABPM questionnaire has been completed. If  $\geq 35$  valid ABPM readings are obtained, they will be processed as described in the manual of procedures.

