  - c. If there is a failed reading, device will attempt three (3) retries ~1 minute apart.
  - d. If participant is consistently getting 2 failed readings, should call the study cellphone
  - e. ABPM cannot get wet
  - f. If they intend to remove the device at any point, please do so between readings
  - g. Payment depends on getting 80% successful readings

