## **IF PARTICIPANT COMPLETED THE ABPM DEVICE FIRST**

17. Check a complete recording (i.e. ~35 BP measurements) was obtained.
  - a. Yes      No
18. If yes, complete the post-ABPM questionnaire.
19. If no, ask the participant to repeat the ABPM. Discuss with participant the challenges they encountered with obtaining a complete ABPM.
20. Ask participant what time he/she anticipates going to sleep tonight and waking up tomorrow
  - a. Anticipated time going to sleep: \_\_\_\_\_
  - b. Anticipated time waking up tomorrow: \_\_\_\_\_
21. Initialize HBPM device. Serial number: \_\_\_\_\_
22. Is the participant's non-dominant arm being used for the WatchBP Home N? Yes      No
23. Reason for not using the non-dominant arm: \_\_\_\_\_
  - a. Put "X" next to cuff sizes that will be used

		HBPM (Microlife WatchBP Home N)	
Cuff Size	Arm circumference	Dominant arm	Non-dominant arm
Small adult	17-21.9 cm		
Med adult	22-32 cm		
Large adult	32.1-42 cm		
Extra-large	42.1-52 cm		
24. Demonstrate to the participant how to place the cuff on their arm
  - a. Find brachial artery (perhaps make small mark)
  - b. Arrow on cuff over brachial artery, non-latex tubing coming out of cuff top
  - c. Bottom of cuff 1" above bend/crease in elbow (if possible)
  - d. Equal tension top and bottom of cuff (1 finger easily, 2 fingers snug, top and bottom)
  - e. Wrap grey non-latex tubing around back of neck
  - f. Connect tubing to HBPM device (make sure it will not pull out)
25. Allow the participant to practice placing the cuff on their arm with you present.
26. Explain to participant the importance of placing the device correctly and initializing the device when they get in bed by holding the on/off button for 3 seconds to start the initial reading and the following readings will occur 2, 3, and 4 hours after they have gone to bed.
27. Take one test reading in 'Usual' mode; repeat until obtain a valid reading (max 3 tries)
  - a. If cannot get a valid reading, check for cuff too loose, kink in tubing, tubing not securely connected to HBPM device; if need be, change cuff and/or HBPM device (be sure to record new serial #)
28. Place the device in 'Nocturnal' mode.
29. Place the device in a carrier bag for the participant.
30. Review with participant:
  - a. Importance of initializing the device before going to bed by holding the on/off button for 3 seconds
  - b. If there is a failed reading, device will attempt three (3) retries ~1 minute apart

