#### **D.10.2. Data transfer.**

**D.10.2.1. ABPM, sleep HBPM, actigraphy, and Device Logs.** Upon return of the ABPM, HBPM, actigraph, and Device Logs, data will be downloaded to a computer and then backed up to a secure network server. Data will be transferred daily to the PEER Unit at UAB using DatAnywhere, a HIPAA compliant file transfer protocol that we used in our AHA-SFRN study. Monthly reports that track data quality will be generated. If data issues are identified (e.g., frequent ABPM or HBPM reading errors), staff will be re-trained.

**D.10.2.2. Echocardiographic measures.** The echocardiographic studies (with unique study identifiers; i.e. de-identified) will be saved to DVD/CD, and backed up to secure research servers at each site. The studies at UAB will be sent to the Cardiovascular Physiology Research Laboratory at Columbia for analysis.

**D.10.3. Data management and cleaning.** All data cleaning will be managed by a statistician at the UAB PEER Unit supervised by [name]. A uniform data editing algorithm, established by Drs. [name] and [name] and used in prior studies, will be implemented to confirm acceptability of the ABPM data and exclude extreme outliers. Minimal editing is the general rule; less than 0.1% of readings are typically excluded. The awake and sleep periods on ABPM will be defined by the actigraphy recording, complimented by self-report

awake and sleep periods from the Device Log. For sleep BP on HBPM, we will confirm that participants were asleep when the the BP readings were obtained using actigraphy data and the HBPM Device Log.

**D.10.4. Minimum number of BP readings required on ABPM and HBPM.** No consensus exists on the number of readings required to consider an ABPM recording complete. Consistent with our prior studies, we will require 14+ awake BP readings, and 5+ sleep BP readings, and  $\geq 80\%$  of the planned 48 readings (39+ total valid readings). We will require three SBP and DBP readings for a sleep HBPM recording to be complete. We will continue recruitment until 600 participants have complete ABPM and sleep HBPM readings.

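### ABPM counts as complete at 35 readings on device return but at 39 or more with awake and sleep minimums in D.10.4, and the Analysis Plan does not say which rule applies

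*Combined protocol and SAP*

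**What the plan says.** **Manual and visit forms.** The Summary of procedures asks staff to "Confirm that at least 35 of planned ABPM readings are valid or all three HBPM readings are valid". For devices picked up or mailed in, "The staff member will check to confirm that at least 35 valid ABPM readings or 3 valid HBPM readings were obtained". The ABPM download procedure sets the repeat trigger: "If at least 35 readings are NOT obtained, ask the participant to repeat the ABPM monitoring period for one night". The Study Visit 3 form says "Check a complete recording (i.e. ~35 BP measurements) was obtained", and the Visit 3 checklist, Visit 4 checklist and Visit 4 form also use about 35. None of these places sets a minimum for awake or sleep readings. On the Visit 2 and Visit 3 forms, participants are told: "Payment depends on getting 80% successful readings".

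**Research plan.** D.10.4 states that "we will require 14+ awake BP readings, and 5+ sleep BP readings", together with at least 80% "of the planned 48 readings (39+ total valid readings". D.6.3.1 offers a repeat whenever the ABPM recording is not complete. D.10.3 defines the awake and sleep periods by actigraphy, supplemented by the device log.

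**Analysis Plan.** Tables 2 to 7, 10, 11, 13 and 14 are limited to participants with complete ABPM or complete sleep data. No reading count is given, so D.10.4 holds the only numeric definition written for analysis.

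**The concern.** The return visit is the last practical chance to replace a poor recording. If the check made there is looser than the definition used later, some recordings are accepted that a repeat might have rescued. If instead the looser check became the analysis definition, nothing in it protects the sleep mean, because 35 readings can be made up almost wholly of daytime ones. Sleep BP on ABPM is the comparator for Hypothesis 2a and an exposure under Hypothesis 3c. Awake BP on ABPM is the reference for Aim 1. Under either reading, the analysis set for the reference standard cannot be reconstructed from the documents.

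**Working it through.** **1. The plan's own figure.** The manual programs readings every 30 minutes day and night, so planned readings = 24 × 60 / 30 = 48. D.10.4 asks for 80%: 0.80 × 48 = 38.4, rounded up to 39. This reproduces the stated 39+.

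**2. The gap in totals.** 35/48 = 72.9%, against 39/48 = 81.3%. Recordings with 35, 36, 37 or 38 readings pass the return check and fail D.10.4.

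**3. The sleep minimum.** With h hours of sleep there are 2h planned sleep readings and 48 − 2h planned awake readings. A recording with T valid readings can hold as few as max(0, T − (48 − 2h)) sleep readings. The sleep lengths below are assumptions.

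| Sleep | Fewest sleep readings, T = 35 | T = 38 | T = 39 |
|---|---|---|---|
| 6 h | 0 | 2 | 3 |
| 7 h | 1 | 4 | 5 |
| 8 h | 3 | 6 | 7 |
| 9 h | 5 | 8 | 9 |

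For example, 35 readings and 7 h of sleep give 35 − 34 = 1. At 6 h, even 39 readings do not guarantee 5 asleep, so the sleep check has to be separate from the total. These are worst cases, reached when the losses fall at night.

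**4. The awake minimum.** The fewest awake readings are T − 2h. At T = 35 this is 23, 21, 19 and 17 for 6, 7, 8 and 9 h of sleep. All exceed 14, so the awake minimum does not bind in a full 48-reading recording.

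**5. Can losses cluster at night?** Table 8 reports removal of the monitor during sleep because of disturbance by 23 participants with ABPM only and 16 with both devices: 39 of 603 (6.5%) for ABPM. How many readings each removal cost is not reported.

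**6. How many recordings lie in the 35 to 38 band?** The documents give no per-reading success rate. As an illustration only, treat the 48 readings as independent with success probability p:

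| p | P(35 or more) | P(39 or more) | Share of accepted recordings with 35–38 |
|---|---|---|---|
| 0.80 | 0.916 | 0.500 | 45% |
| 0.85 | 0.991 | 0.826 | 17% |
| 0.90 | 0.9998 | 0.981 | 1.9% |
| 0.95 | 1.000 | 0.9999 | 0.01% |

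The range is too wide to support an estimate.

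**7. The reported analysis sets.** 603 − 569 = 34 (5.6%) are absent from Table 2, and 603 − 547 = 56 (9.3%) from Table 7. Table 9 (both clinic BPs and LVMI) has 587, and Table 10 (unattended BP, awake ABPM and LVMI) has 554. So at least 587 − 554 = 33 people with full clinic BP lacked usable awake ABPM data. The Table 2 shortfall is therefore almost all on the ABPM side, but nothing shows whether those recordings were absent, failed, or excluded under a completeness rule. Table 7 also needs complete HBPM data.

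**The case against.** The strongest reply is that D.10.4 belongs to a research plan written as a funding request and was overtaken in practice. It names a different ABPM device (SpaceLabs 90227, against WatchBP O3 in the manual), and the manual departs from it on other operational points. If 35 was the working rule throughout, no accepted recording was later excluded. This stands as far as it goes. A reader might infer that recordings accepted in clinic were in fact discarded, and the documents do not support that, because no section says D.10.4 governed the reported analysis. Equally, no section says it was superseded, and under the 35-reading rule the sleep mean has no minimum behind it.

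Other replies:

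- The 80% payment wording is an incentive told to participants. It does not have to equal the repeat trigger and is not a third acceptance rule. This is fair.
- D.10.4 itself says there is no consensus on the number of readings. That bears on which threshold to choose, not on having two.
- D.11.1 allows multiple imputation. The Analysis Plan nevertheless restricts each table to complete cases, so imputation does not remove the problem.
- The results tables are already filled, so rewording the trigger recovers nothing for those participants. This is correct, and for those data the remedy is disclosure and sensitivity analysis.

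**Conclusion.** The conflict is established from the text: 35 or about 35 readings with no sleep check at return, 39 or more with 14 awake and 5 asleep in D.10.4, and no count in the Analysis Plan. Only some accepted recordings are affected: those with 35 to 38 readings, and those with fewer than 5 sleep readings. The awake minimum adds nothing in a full recording.

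The number affected is unknown. A reader might take the 34 and 56 missing participants as the size of the loss. That is not supported: the causes are not reported, and the 56 also reflects HBPM. The sleep examples assume 48 planned readings, the sleep lengths shown, and losses concentrated at night. The point should be put right, but it does not by itself show that any reported result is wrong.

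**What to change.** **Documents.** Use one ABPM completeness definition in the manual (Summary, pick-up and mail returns, download procedure), the Visit 3 and 4 checklists and forms, D.10.4 and the Analysis Plan. The return check should include the sleep-reading minimum: a provisional count from the device log at download, then confirmation by actigraphy plus log as in D.10.3. A log-only count is not the analysis definition, so some recordings could still be reclassified.

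**Data already collected.**

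- State which rule produced N=569 and N=547. D.15 promised to post variable-derivation code before analysis, so that code should answer this.
- Report how many recordings had 35 to 38 readings, and how many had fewer than 5 sleep readings.
- Show Tables 2 to 7, 10, 11, 13 and 14 under both D.10.4 and the 35-reading rule. Label any change of analysis set as made after results were seen.

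**Cost.** Wording changes, and a re-derivation from the stored ABPM Excel reports with the actigraphy and logs. For any further recruitment there would be some additional optional repeats, in unknown number. Each repeat adds ABPM exposure before the tolerability questionnaire used for Hypothesis 2b, so repeats should be flagged in that analysis.
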